7.0 STUDY INTERVENTIONS

1) 1,25(OH)₂D₃. As per Drug Bank., this agent is used to treat vitamin D deficiency or insufficiency, refractory rickets (vitamin D resistant rickets), familial hypophosphatemia and hypoparathyroidism, and in the management of hypocalcemia and renal osteodystrophy in patients with chronic renal failure undergoing dialysis. This protocol will use doses that are identical to those used for these other clinical indications.

Also, as per Drug Bank, the first pathway involves 24-hydroxylase activity in the kidney; this enzyme is also present in many target tissues which possess the vitamin D receptor such as the intestine. The end product of this pathway is a side chain shortened metabolite, calcitroic acid. The second pathway involves the conversion of calcitriol via the stepwise hydroxylation of carbon-26 and carbon-23, and cyclization to yield ultimately 1α,25R(OH)₂-26,23S-lactone D₃. The lactone appears to be the major metabolite circulating in humans. Enterohepatic recycling and biliary excretion of calcitriol occur. The metabolites of calcitriol are excreted primarily in feces. Cumulative excretion of radioactivity on the sixth day following intravenous administration of radiolabeled calcitriol averaged 16% in urine and 49% in feces.

Patient instructions: Patients will be instructed to take 1 tablet/placebo once per day.

2) Inspiratory isometric resistance exercise. Patients will be provided with a power breath device and will be instructed on how to use it. Inspiratory muscle resistance training involves subjects being exposed to 10-15 minutes of training per day each day for 8 weeks using a commercially available inspiratory threshold-training device. Subjects will be asked to gradually increase training to 20-30 minutes per day or two 15 minute sessions. (<https://www.usa.philips.com/healthcare/product/HCHS730010/treshold-inspiratory-muscle-trainer>). The inspiratory muscle training groups will breathe against a resistance set to generate 30% of P_I_{max} (as estimated by a “sniff” test). Patients in the sham group will train daily against a resistance set to only 15% P_I_{max}.

Method for Assigning Subjects to Treatment Groups.

Patients will be randomly assigned to one of the 4 treatment arms with stratification based on the following:

- 1) sex: male versus female
- 2) patient-reported degree of weight loss in the preceding 3 months: ≥5% versus < 5% (or no weight loss).
- 3) patient reported history of pneumonia in the past five years: yes or no

Preparation and Administration of Study Drug.

The Mayo Clinic Pharmacy will generate 1,25(OH)₂D₃ tablets 0.25 micrograms along with identical placebo. Assignment will remain blinded to patients, healthcare providers, and members of the study team who have direct patient contact.

A member of the study team who has no patient contract will set the resistance on the inspiratory; the resistance gauge will then be effaced with rubbing alcohol.

Monitoring.

	Baseline (within 14 days of registration to study)	2 weeks (+/- 7 days)	4 weeks (+/- 7 days)	8 weeks from last visit (+/- 7 days)	Total blood volume
history and physical examination	X		X	X	
laboratory results (creatinine, bilirubin, CDHVD 1,25 Dihydroxy D2 and D3, transaminase, alkaline phosphatase)	X				5ml
SNIP, MIP and MEP tests	X	X	X	X	
Laboratory results Calcium and phosphorous	X	X	X	X	1ml each time point
Questionnaires*		X	X	X	

*adherence questionnaire and arm assignment questionnaire (see Appendix 1)

SAMPLE SIZE AND STATISTICS. A total of 15 patients per arm (60 total) will be included in this study. This sample size is based on precedent from other trials that were aimed at obtaining data on point estimates of efficacy and standard deviations. All data, including patient demographics and adherence data, will be presented descriptively with means, medians, percentages, ranges, standard deviations, and 95% confidence intervals, as appropriate. All data will nonetheless be generated and summarized with the goal of publication. In a highly exploratory manner, we will report the data described below within the context of study arm assignment; however, comparisons between arms will not be presented as primary outcome data but as highly exploratory, non-primary, non-secondary analyses.

Definition of Endpoints. All patients will undergo a sniff test at baseline, 2 weeks , 4 weeks and at 8 weeks. As described earlier, patients will be asked to perform the test 10 times; the best and worst measurements will be recorded.

1) Primary endpoint. These sniff test readings and the descriptive presentation of these data will be the primary endpoint of this trial.

2) Secondary endpoint. Patients will also be provided with an adherence questionnaire that they will be completed at the end of 8 weeks; this questionnaire has been used extensively by our group in prior studies and will serve as a secondary endpoint for this trial [30-32].

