4.0 STUDY DESIGN

This is a randomized, double-blinded dummy pilot study design (n=60 with 15 patients to be assigned to each study arm):

PRIMARY STUDY ENDPOINT: To acquire descriptive data on the SNIFF after 8 weeks of the above interventions.

SECONDARY STUDY ENDPOINT: To acquire data on the safety of inspiratory isometric resistance and 1,25(OH)₂D₃

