6.0 PATIENT ELIGIBILITY [30-32]

Eligibility Criteria:

1) 18 year of age or older

2) diagnosis of cancer

3) renal and hepatic function (creatinine $\leq 2 \times$ the institutional upper limit of normal; bilirubin $\leq 2 \times$ the institutional upper limit of normal)

4) no contraindication to receive either of the planned interventions of inspiratory resistance training or 1,25(OH)₂D₃ in the opinion of the healthcare provider

5) no difficulties with swallowing oral medications in the opinion of the enrolling physician (no documentation necessary in the medical record).

Contraindications:

- 1) Patient is taking calcium or vitamin D supplements and is unwilling to stop for 8 weeks
- 2) Severe chronic obstructive pulmonary disease (oxygen dependent or patient self-reports unable to walk one block without difficulty
- 3) Calcium or phosphorous level above the institutional upper limit of normal

Subject Recruitment:

Patients will be recruited from all the clinical facilities at the Mayo Clinic in Rochester, Minnesota. The study team will rely on referrals from healthcare providers.

Early Patient Withdrawal: Patients can withdraw from the study at any time based on their wishes. In the event that an intervention-related adverse event occurs, patients will be withdrawn from the study by the study team.

Patients who develop an increase in their calcium or phosphorous level above the institutional baseline will be taken off the study agent/placebo and referred to their primary healthcare provider. Patients will be given the option to continue on with the inspiratory resistance training to complete the eight week training period.

Human Subjects

1. Risks to the subjects

Human Subjects Involvement and Characteristics: All protocols and all techniques to be used will be approved by the Mayo Clinic Institutional Review Board prior to initiation of any studies. Subject characteristics and inclusion/exclusion criteria have been clearly specified above. Our plan is to complete the study on 60 participants with 15 in each group. We are anticipating a target accrual of 75 subjects to account for anticipated dropout. In order to have 60 participants complete the study.

Sources of Materials: Samples of blood, obtained during the study will be used exclusively for research purposes.

Potential Risks: The following are the potential risks for this study:

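### Allocation is stratified on sex, weight loss and pneumonia history, but the statistics section never uses these factors, so any exploratory SNIP contrast would have conservative intervals

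*Combined protocol and SAP*

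**What the plan says.** Under Method for Assigning Subjects to Treatment Groups (Section 7.0), the protocol says: "Patients will be randomly assigned to one of the 4 treatment arms with stratification based on the following". The three factors are "sex: male versus female", "patient-reported degree of weight loss in the preceding 3 months: ≥5% versus < 5% (or no weight loss" and "patient reported history of pneumonia in the past five years: yes or no". No block size, minimisation scheme or allocation ratio is given.

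The Sample Size and Statistics paragraph does not mention the factors. It plans descriptive summaries with 95% confidence intervals and says that "we will report the data described below within the context of study arm assignment". Comparisons between arms are classed there as highly exploratory, neither primary nor secondary. Section 3.0 nevertheless sets objectives on the separate and combined effects of the two interventions. It says the work should supply point estimates and standard deviations for those effects, and the endpoint definitions look ahead to a larger trial.

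The number per arm appears in three forms:
- Section 4.0: "n=60 with 15 patients to be assigned to each study arm".
- Section 6.0: "Our plan is to complete the study on 60 participants with 15 in each group", from a target accrual of 75.
- Statistics paragraph: "A total of 15 patients per arm (60 total) will be included in this study".

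**The concern.** Stratifying on a factor makes the arms alike on it, so the true sampling variance of an arm difference no longer contains the part of the outcome variance that the factor explains. An unadjusted analysis still counts that part in its standard error. The point estimate is not biased, but its interval is wider than it should be.

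Two things are at stake. The first is the precision of exploratory contrasts in a trial with 15 patients per arm. The second is the SD handed to the larger trial. An SD that ignores the factors includes variance that an adjusted analysis would remove, so a later trial that adjusts would be planned too large.

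**Working it through.** **Inputs from the documents.** Four arms, three two-level factors, 15 per arm and 60 in total, 75 accrued.

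**Assumed inputs (no figure in the documents).** R², the share of within-arm SNIP variance explained by the three factors: 0 to 0.3. For the side note on allocation, prevalences of 50% for sex, 30–50% for weight loss of at least 5%, and 10–50% for pneumonia history.

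**The plan's own figures.** 4 × 15 = 60, which agrees. The accrual of 75 implies dropout of 1 − 60/75 = 20%, a rate the protocol does not state. The 15 per arm rests on precedent, so there is no power calculation to reproduce.

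**Effect of leaving the factors out.** With the factors balanced across arms:
- width ratio, unadjusted to adjusted = 1/√(1 − R²)
- coverage of the unadjusted nominal 95% interval = 2Φ(1.96/√(1 − R²)) − 1
- ratio of residual SD to raw SD = √(1 − R²)

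| Assumed R² | Width ratio | Coverage | Residual SD / raw SD |
|---|---|---|---|
| 0 | 1.00 | 95.0% | 1.00 |
| 0.1 | 1.05 | 96.1% | 0.95 |
| 0.2 | 1.12 | 97.2% | 0.89 |
| 0.3 | 1.20 | 98.1% | 0.84 |

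Required sample size scales with SD². Planning an adjusted trial from the raw SD would therefore inflate it by 1/(1 − R²), which is 1.11 at R² = 0.1 and 1.43 at R² = 0.3.

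**Cost of adjusting if R² = 0.** In a four-arm model on 60 patients, residual degrees of freedom fall from 60 − 4 = 56 to 53. The t multiplier rises from 2.003 to 2.006, a ratio of 1.001. Chance imbalance in the factors adds a little. Simulated with blocks of 4 or 8 within strata and assumed prevalences of 50%, 50% and 20%, the adjusted interval for a two-arm difference is on average 0.6% or 1.0% wider.

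**Side note: allocation.** 2 × 2 × 2 = 8 strata, and 8 × 4 = 32 cells, so 60/32 = 1.9 patients per cell. If blocks within strata were used for 60 patients, simulation over the assumed prevalences gives:

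| Block size | Exactly 15 in every arm | Mean gap, largest minus smallest arm |
|---|---|---|
| 4 | 5–7% of trials | 2.6 |
| 8 | 2–3% of trials | 3.3–3.7 |

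The cost is small. A 13 v 17 split changes the SE of a difference by √(1/13 + 1/17)/√(2/15) = 1.009, and 12 v 18 by √(1/12 + 1/18)/√(2/15) = 1.021. Minimisation on the three margins gives exact 15s in 22–26% of trials at an assignment probability of 0.8, and in 64–68% if deterministic.

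**Side note: which 15.** If 75 are randomised as 19/19/19/18 with an assumed independent dropout of 20%, all four arms end with exactly 15 completers in about 0.2% of trials, and with at least 15 in about 15%. On the completer reading, dropout alone prevents exact 15s, whatever the allocation method.

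**The case against.** The strongest reply is that there is no defect to correct. The primary endpoint is a descriptive presentation of sniff readings. Arm comparisons are expressly set apart as highly exploratory, and no contrast model is written down that could be wrong. Leaving the factors out makes intervals conservative, not misleading. The size quoted depends on an R² that nobody has measured. Much of this stands, and it is why the point is minor. It does not remove the point: exploratory comparisons will be reported, and Section 3.0 wants effect estimates and SDs.

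Three stronger readings are tempting, and the documents do not support them.
- *The stratification defeats the stated 15 per arm.* A reader might infer this from the 32 cells. But the protocol names no allocation method, so blocks within strata are an assumption and minimisation is not excluded. Unequal arms would cost only about 1–2% in precision, and Section 6.0 treats 15 as completers out of 75.
- *The benefit of stratifying is lost.* Balance of the factors across arms remains, and a by-arm descriptive report uses it.
- *The planned results are biased or invalid.* Within-arm summaries are unaffected, and unadjusted contrasts remain unbiased.

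The reference list includes a paper on how many stratification factors are too many, but no citation of it was found in the protocol text. It does not show which method will be used.

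**Conclusion.** The point holds as a minor improvement to the analysis. The trial randomises on three factors and its statistics section does not use them. Any exploratory SNIP contrast computed without them would have an interval about 5% to 20% too wide, covering about 96% to 98%, if R² is 0.1 to 0.3. If the factors explain nothing, adjusting gains nothing and costs about 1%.

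These figures rest on the assumed R² and on good balance of the factors across arms; with poorer balance, unadjusted coverage lies nearer 95%. If the outcome is change from baseline, or baseline SNIP is also in the model, the factors may explain less and the gain shrinks.

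The unstated allocation method is missing detail, not an error. The three descriptions of 15 per arm are a wording inconsistency that needs reconciling.

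**What to change.** 1. Add to the statistics section that any exploratory SNIP contrast between arms, or for either intervention across arms, is fitted with sex, weight loss and pneumonia history as main effects. The effect estimate and residual SD carried forward to the larger trial come from the same model. Leave the within-arm descriptive summaries as they are. Cost: one sentence and 3 degrees of freedom; no new data, visits or patients.
2. Name the allocation method, with block size if blocks are used. Cost: one sentence.
3. Reconcile Section 4.0, Section 6.0 and the statistics paragraph on whether 15 per arm means assigned, completed or included, and how that relates to 75 accrued (75 does not divide equally by 4). Cost: wording only.

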5.0 IDENTIFICATION OF SOURCE DATA

The following source data will be directly recorded on case report forms:

- Vital signs at baseline and at 8 weeks
- Bilirubin, creatinine, serum calcium and phosphorous at baseline
- SNIP TEST results at baseline, 2, 4 and 8 weeks
- MIP and MEP TEST results at baseline, 2, 4 and 8 weeks
- Serum calcium and phosphorous levels at 2,4, and 8 weeks
- Adverse events

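### The monitoring table times the final visit from the last visit, which read literally gives about week 12 and contradicts the 8-week final assessment stated everywhere else

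*Combined protocol and SAP*

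**What the plan says.** The Monitoring table in Section 7.0 has four visit columns. The first is "Baseline (within 14 days of registration to study". The second and third are at 2 and 4 weeks, each with a window of 7 days either way. The fourth is headed "8 weeks from last visit (+/- 7 days". The SNIP, MIP and MEP tests, the calcium and phosphorous results and the questionnaires are all marked in that fourth column.

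The rest of the document places the final assessment at 8 weeks:

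- Section 4.0, primary endpoint: "To acquire descriptive data on the SNIFF after 8 weeks of the above interventions".
- Section 5.0, source data: "SNIP TEST results at baseline, 2, 4 and 8 weeks", with the same time points for MIP and MEP, and calcium and phosphorous at 2, 4 and 8 weeks.
- Section 7.0, Definition of Endpoints: "All patients will undergo a sniff test at baseline, 2 weeks , 4 weeks and at 8 weeks". The adherence questionnaire is due when the 8 weeks are over.
- Section 7.0, item 2: "10-15 minutes of training per day each day for 8 weeks". Section 6.0, on patients who come off the tablets, lets them go on "to complete the eight week training period".

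The Definition of Endpoints then makes the whole set of readings primary: "These sniff test readings and the descriptive presentation of these data will be the primary endpoint of this trial". Nowhere is the last visit defined, the start of training fixed relative to baseline or registration, or a post-treatment follow-up visit described.

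**The concern.** Three of the four column headers can be read as times on one clock. The fourth counts from another visit, and the visit before it is the 4-week visit. Taken at its word, the header moves the final assessment well past the end of an 8-week intervention.

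Section 3.0 says that the study exists to supply estimates and standard deviations for the effect of 8-week interventions on the sniff test, and Section 7.0 looks ahead to a larger trial. A final reading taken weeks after training stops describes how far any gain persists, not the gain at 8 weeks. If some staff read the header as week 8 and others as week 12, two time points are pooled under one label. With 15 patients per arm and a descriptive analysis, nothing later in the plan would detect or correct that.

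The last calcium and phosphorous check sits in the same column and inherits the same ambiguity.

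**Working it through.** The check is calendar arithmetic, in weeks from the start of the visit clock.

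**Inputs.** The preceding visit is at week 4 ± 1 (Monitoring table). The step to the final visit is 8 ± 1 weeks (same table, last column). Training lasts 8 weeks (Sections 6.0 and 7.0). The final sniff test in the text is at week 8 (Sections 4.0 and 5.0, Definition of Endpoints).

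**1. The text's own figure.** Counting 8 weeks from baseline or from the start of intervention: 0 + 8 = week 8. With the 7-day window: 8 − 1 = 7 to 8 + 1 = 9. This is 8 − 4 = 4 weeks after the 4-week visit and coincides with the end of training.

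**2. The table read literally.** Final visit = preceding visit + step.

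| | Preceding visit | Step | Final visit |
|---|---|---|---|
| Earliest | 3 | 7 | 10 |
| Nominal | 4 | 8 | 12 |
| Latest | 5 | 9 | 14 |

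The ranges 7 to 9 and 10 to 14 do not overlap, so the visit windows cannot absorb the difference.

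**3. Gap between the end of training and the final reading.** Gap = final visit − (training start + 8).

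| Assumed training start | Training ends | Gap: earliest / nominal / latest |
|---|---|---|
| Week 0 (same clock) | Week 8 | 10 − 8 = 2 / 12 − 8 = 4 / 14 − 8 = 6 |
| Week 2 | Week 10 | 10 − 10 = 0 / 12 − 10 = 2 / 14 − 10 = 4 |

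Both starts are assumptions, because the documents do not give one. Two weeks was tried because it is the width of the baseline window. The undefined start also affects the text's schedule: with a two-week delay, a visit at week 8 of the clock falls after 8 − 2 = 6 weeks of training.

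**4. Effect of mixed readings (illustration only).** Suppose half of the final readings are taken at each time, the true means differ by d standard deviations, and the within-time SD is 1. The pooled mean moves by d/2 and the variance rises by d²/4.

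- d = 0.5: SD = √(1 + 0.0625) = 1.03, about 3% larger.
- d = 1: SD = √(1 + 0.25) = 1.12, about 12% larger.

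The even split and the values of d are assumptions. The documents give no data on loss of strength after training stops.

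**5. Share of the primary endpoint affected.** There are four sniff-test time points: baseline and weeks 2, 4 and 8. Only the last depends on this header.

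**The case against.** The strongest answer is that this is one stray header in an otherwise consistent document. The design section, the source-data list, the endpoint definition and the training description all say 8 weeks, and no week-12 visit is described anywhere. There is one institution and one study team, so divergent readings are possible but not shown. The study is a descriptive pilot: no test or power calculation depends on the header, and the 60 completers and accrual target of 75 are untouched. All of this stands, and it limits the point to an internal contradiction. It does not remove it. The table is the only place that gives visit windows, and the text's schedule can be recovered from it only by reading the last visit as baseline, which the header does not say.

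A reader might infer more than the documents support:

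- *That a 12-week assessment is intended, or will certainly happen.* The surrounding text points the other way.
- *That every primary endpoint reading is affected.* The Definition of Endpoints counts all the sniff readings, and those at baseline and weeks 2 and 4 are sound.
- *That the delay after training is firmly 2 to 6 weeks.* That needs a common start for training and the visit clock, which is not stated.
- *That patients would spend 8 weeks on treatment without a calcium or phosphorous result.* If the intervention ends at week 8, the on-treatment stretch after the week-4 result is 8 − 4 = 4 weeks on either reading. What the literal reading loses is the week-8 check listed in Section 5.0.

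**Conclusion.** The point holds as a contradiction about when the final assessment takes place. As written, the table header gives nominal week 12 (range 10 to 14), against week 8 (range 7 to 9) in the rest of the document. It is most likely a drafting slip, and the documents do not show that a later visit was meant.

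If the table were followed, each patient's final SNIP, MIP and MEP readings would fall nominally 4 weeks after training ends, with a range of 2 to 6 weeks if training and the visit clock start together. The range would be 0 to 4 weeks if training starts two weeks later. If staff differed in their reading, two time points would be mixed under one label. One of four sniff time points is at stake, but it is the one that Section 4.0 names as the primary endpoint. Sample size is not affected. The header is wrong as written and cheap to correct.

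**What to change.** Reconcile the last column header with Section 4.0, Section 5.0 and the Definition of Endpoints. Define one day zero, for example the start of intervention, and time the 2-, 4- and 8-week SNIP, MIP and MEP tests and questionnaires from it. Keep the 7-day window.

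That window lets the final visit fall up to a week either side of the end of training. A further rule that the test must be done within the 8-week period would therefore conflict with it. Instead, record the actual date of the final SNIP relative to the last training day, so that the timing can be described alongside the results.

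The calcium and phosphorous check in the same column must be reconciled with the 2, 4 and 8 weeks in Section 5.0. How that is settled is for the sponsor and the clinical team.

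The cost is a short amendment: revised column headers, one definition of day zero, and the date of the last training day on the case report form if it is not already collected. No patients, visits or assays are added.

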3.0 STUDY OBJECTIVES

3.1 To explore the effect of inspiratory muscle resistance training on inspiratory muscle strength.

[figure not shown]
3.2 To explore the effect of 1,25(OH)₂D₃ administration on inspiratory muscle strength.

3.3 To explore the combined effect of inspiratory muscle resistance training and 1,25(OH)₂D₃ administration on inspiratory muscle strength.

In short, this work is intended to provide point estimates and standard deviations for the effects of an 8-week interventions on the “sniff test” as described in the 4-arm study below.

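### The pilot exists to estimate intervention effects on the sniff test, but the plan prespecifies no effect estimate and leaves baseline SNIP and the stratification factors unused

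*Combined protocol and SAP*

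**What the plan says.** Section 3.0 (Study Objectives) sets three aims, and each is an effect. Objective 3.1 reads "To explore the effect of inspiratory muscle resistance training on inspiratory muscle strength". Objective 3.2 asks the same question of the vitamin D metabolite, and 3.3 asks it of the two given together.

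With the sniff test as the measure, the section then sums up its purpose: "this work is intended to provide point estimates and standard deviations for the effects of an 8-week interventions". The sample size paragraph in section 7.0 justifies 15 per arm by precedent from trials that sought point estimates of efficacy and SDs.

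The endpoint and analysis text is narrower. Section 4.0 makes descriptive SNIFF data after 8 weeks the primary endpoint. Definition of Endpoints makes the readings and their descriptive presentation primary. The sample size paragraph plans means, medians, ranges, SDs and 95% CIs, and reporting by arm in an exploratory manner. It adds that "comparisons between arms will not be presented as primary outcome data but as highly exploratory, non-primary, non-secondary analyses".

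The data for a sharper analysis are collected. SNIP is measured at baseline, 2, 4 and 8 weeks, with the best and worst of 10 attempts recorded. On allocation the plan says "Patients will be randomly assigned to one of the 4 treatment arms with stratification based on the following", and lists sex, recent weight loss and pneumonia history. None of these, nor baseline SNIP, is given a role in the analysis.

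**The concern.** In a trial with sham training and an identical placebo, the effect of an intervention is a contrast with its control. Sniff readings within one arm mix any effect with the course of the disease and with practice on an effort-dependent test done 10 times at each of four visits. The controls remove these only when arms are compared. The plan recognises the issue: its rationale for the arm-guess questionnaire cites improvement on placebo in 30-40% of cancer patients.

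The quantity that the pilot exists to supply therefore has neither primary nor secondary status and no stated method. The contrast, the covariates and the choice between best and worst sniff could all be settled after the data are seen, in a study meant for publication and for planning a larger trial. The simplest analysis by arm would also give up precision that the collected data could provide at no extra cost.

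**Working it through.** **The plan's own figures.** 4 × 15 = 60 agrees with the stated total. Accrual of 75 for 60 completers implies 20% dropout, since 60/(1 − 0.20) = 75; no rate is stated. The 15 per arm cannot be derived, because no effect size, SD, alpha or power is given. No stated figure is shown to be wrong.

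**Inputs for precision.**
- 15 per arm and four arms (section 7.0).
- The layout is read as 2×2 (training 30% v sham 15%, agent v placebo) from the objectives, the sham and the placebo. The documents do not use the word factorial, and a figure in section 3.0 is not shown. On this reading each factor is given to 30 of 60 patients.
- The SNIP SD is not in the documents, so results are in units of the week-8 SD.
- The correlation r between baseline and week-8 SNIP is not in the documents. It is assumed to be 0.5 to 0.8.
- All 60 completers have week-8 data.

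**Formula.** 95% CI half-width = t(0.975, df) × √(variance factor), multiplied by √(1 − r²) when adjusted for baseline.

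| Estimate | Calculation | Half-width (SD) |
|---|---|---|
| Two arms, 15 v 15, unadjusted | t(28) × √(2/15) | 0.75 |
| Same, variance pooled over four arms | t(56) × √(2/15) | 0.73 |
| Margin, 30 v 30, unadjusted | t(56) × √(2/30) | 0.52 |
| Margin, adjusted, r = 0.5 | t(52) × √(2/30) × 0.866 | 0.45 |
| Margin, adjusted, r = 0.7 | t(52) × √(2/30) × 0.714 | 0.37 |
| Margin, adjusted, r = 0.8 | t(52) × √(2/30) × 0.600 | 0.31 |
| Interaction, unadjusted | t(56) × √(4/15) | 1.03 |

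The 52 df are 60 less 8 parameters: intercept, two factors, their interaction, baseline and three stratum terms. The three stratum terms cost almost nothing; at r = 0.7 the half-width is 0.37 with or without them.

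**Worth in patients.** Adjustment of the margin: (0.52/0.45)² = 1.3 at r = 0.5, and (0.517/0.311)² = 2.8 at r = 0.8.

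**Why ANCOVA and not change scores.** A change score multiplies the half-width by √(2(1 − r)): 1.00, 0.77 and 0.63 at r = 0.5, 0.7 and 0.8. ANCOVA gives 0.87, 0.71 and 0.60, which is smaller each time.

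**The SD for the larger trial.** From chi-square limits, the 95% CI for an SD runs from 0.73 to 1.58 times the estimate with one arm (14 df). With the four arms pooled (56 df) it runs from 0.84 to 1.23 times, and with the ANCOVA residual (52 df) from 0.84 to 1.24 times. The gain comes from pooling, not from the covariates. What adjustment may add is a smaller residual SD.

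**The case against.** The strongest reply is that this is a pilot. Every objective is worded as exploration, the primary endpoint is openly descriptive, and exploratory comparisons suit exploratory aims. Much of this stands. A primary endpoint without hypothesis tests is defensible at 60 patients, and no test is asked for here. It does not answer the absence of a prespecified effect estimate, which section 3.0 promises.

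A reader might infer more than the documents support:

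- **That the pilot cannot deliver its estimates, or answers none of 3.1 to 3.3.** Between-arm comparisons are given a low rank, not excluded. Means, SDs and CIs are planned, with reporting by arm, so unadjusted differences, and even the 30 v 30 margins, can be derived.
- **That the change is worth about four times the patients.** Going from 15 v 15 unadjusted to the adjusted margin gives (0.748/0.370)² = 4.1 at r = 0.7, but 2.8 at r = 0.5 and 5.8 at r = 0.8. This mixes the gain from the margin with that from adjustment, and the two contrasts estimate the same effect only if the interventions do not interact.
- **That ANCOVA is what makes the SD usable.** Pooling the planned arm SDs does that.
- **That regression to the mean distorts the readings.** Section 6.0 does not select patients on respiratory strength, so the documents give no mechanism for it. Practice and disease course remain.

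**Conclusion.** The mismatch is real but moderate: the stated purpose is effect estimates with SDs, and the plan specifies none. The loss is of prespecification and precision. The unadjusted two-arm half-width of 0.75 SD compares with 0.52 for the margin and 0.31 to 0.45 for the adjusted margin.

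This rests on the 2×2 reading, 60 patients with week-8 data and an assumed r of 0.5 to 0.8. Fewer completers would widen every interval. The interaction, at 1.03 SD unadjusted, can only be described, so 3.3 stays imprecise under any analysis. No stated figure is wrong and the needed data are already collected. This should be fixed before the data are analysed.

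**What to change.** Keep the descriptive framing, the by-arm table and the absence of p-values. Add one paragraph to the statistics section:

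1. Name the SNIP reading to be analysed (best or worst of the 10).
2. Prespecify one estimation-only ANCOVA of week-8 SNIP on training, agent, baseline SNIP and the three stratification factors, stating that the four arms are treated as a 2×2 layout.
3. Report, each with a 95% CI, the two marginal effects. From the model with the interaction term, report the combined v double-control contrast (the direct reading of 3.3), the interaction and the four adjusted cell means.
4. Report the SD pooled over arms, raw and residual, and the baseline to week-8 correlation, for planning the larger trial.
5. Analyse patients as randomised and state how many have week-8 data, or use the 2- and 4-week readings in a repeated-measures version.

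The cost is a paragraph of text and one model, with no new visits, patients or measurements. The downside is that the margins are average effects if the interventions interact, which is why the cell means and the interaction are shown beside them.
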